Antidepressant medications are commonly prescribed in the USA not only for depression, but also for anxiety disorders such as generalized anxiety disorder and obsessive-compulsive disorder, premature ejaculation, post-traumatic stress disorder, and neuropathic pain. In fact, prescriptions for antidepressants in American men increased by 28% between 2000 and 2010 (Medco, 2010). Despite being widely prescribed in the United States in men of reproductive age, the impact of antidepressants on fertility has not been extensively studied. After noticing worsened semen parameters in men on anti-depressants (Tanrikut and Schlegel 2007), the investigators performed the first prospective study to demonstrate a deleterious impact of selective serotonin reuptake inhibitors (SSRI) on sperm DNA integrity, which has been linked to reproductive outcomes (Tanrikut and Schlegel, 2010). Further small studies have corroborated the negative impact of SSRIs on male fertility, as assessed by semen parameters and/or sperm DNA integrity (Safarinejad, 2008 and Koyuncu et al, 2011). While the exact mechanism for the negative impact of SSRIs on male fertility is not yet known, animal studies have suggested the potential spermicidal action of SSRIs mediated through the binding of SSRIs to sulfhydryl groups on spermatozoa (Wolf et al, 1992; De Lamirande et al., 1998, and Kumar et al., 2006). Tanrikut and Schlegel suggested an impact on post-testicular sperm transport as the mechanism for sperm DNA damage (Tanrikut and Schlegel, 2010). An increase in sperm DNA fragmentation commonly occurs in men with delayed sperm transport, as has been shown in those with ejaculatory dysfunction or obstructive azoospermia. No studies have examined the impact of a newer, but similar, class of antidepressant - the serotonin-norepinephrine reuptake inhibitor (SNRI). Like SSRIs, SNRIs inhibit the reuptake of serotonin, but also act on norepinephrine. The use of SNRIs has increased recently due to their slightly improved efficacy profile when compared to SSRIs. Duloxetine (trade name Cymbalta) is an SNRI and is one of the most commonly prescribed anti-depressants in the United States. The most common side effects for duloxetine at its optimal treatment dose of 60mg daily include nausea (23-25%), dry mouth (13-15%), headache (13-14%), somnolence (10-12%), and fatigue (10-11%). Significant side effects include the activation of mania/hypomania in those with bipolar disorder and the potential for serotonin syndrome in those concurrently taking SNRIs with other serotonergic medications.

Primary and Secondary Objectives

The primary objective of the research study is to determine the administration of duloxetine on sperm DNA fragmentation, and the secondary objective is to determine the impact of duloxetine administration on semen parameters such as serum hormone levels, and sexual function.

Study Design

The hypothesis is that administration of duloxetine will result in a deterioration in sperm DNA fragmentation in healthy, fertile men. To evaluate the hypothesis, the investigators conducted a placebo-controlled, randomized control trial with duloxetine in healthy, fertile men not previously on any antidepressants. Patients will be randomized to either the duloxetine (60mg PO daily) or placebo groups for 6 weeks. In the sixth and last week of therapy, the drug dosage will be halved to 30mg PO daily as a taper. Changes in sperm DNA fragmentation were assessed at numerous time points before, during, and after drug administration (semen analyses at baseline before administration, at 2-weeks, 6-weeks, and then at 2-weeks and 4-weeks after drug cessation). Other outcomes measured include semen parameters (sperm concentration, motility, morphology), hormone levels (testosterone, estrogen, prolactin, LH, FSH collected at baseline, at 2-weeks, 6-weeks, and at 2-weeks and 4-weeks after discontinuation of medication), and sexual function (IIEF and MSHQ) surveys (collected at baseline, at 6-weeks, and at 4-weeks after discontinuation of medication).

Methods

Selective serotonin reuptake inhibitors (SSRI) are known to affect post-testicular sperm transport and adversely impact male fertility, but no studies have examined the impact of a newer, but similar, class of antidepressant - the serotonin-norepinephrine reuptake inhibitor (SNRI). Duloxetine (trade name Cymbalta) is an SNRI and is one of the most commonly prescribed anti-depressants in the United States. An increase in sperm DNA fragmentation commonly occurs in men with delayed sperm transport, as has been shown in those with ejaculatory dysfunction or obstructive azoospermia. The research hypothesis is that administration of duloxetine will result in a deterioration in sperm DNA fragmentation in healthy, fertile men. To test the hypothesis, a placebo-controlled, randomized control trial will be conducted with duloxetine in healthy, fertile men not previously on any antidepressants. Patients will be randomized to either the duloxetine or placebo groups for 6 weeks. Changes in sperm DNA fragmentation will be assessed at numerous time points before, during, and after drug administration. Other outcomes measured will include semen parameters (sperm concentration, motility, morphology), hormone levels (testosterone, estrogen, prolactin, LH, FSH), and sexual function (IIEF and MSHQ) surveys.

Study Population

Study participants will be screened and recruited if they meet the selection criteria. Participants who are healthy males aged 18-65 years, with normal or borderline (concentration >10 million/mL, motility >30%, morphology >3%) semen parameters on semen analysis, and are willing to engage in sexual activity, alone or with a partner, at least weekly for the duration of the study, and are capable of providing semen sample will be included in the study. Participants will be excluded if they have clinically detected varicocele, diagnosed with oligoasthenospermia or azoospermia on screening semen analysis, ongoing attempts to initiate pregnancy, current sexual dysfunction, indicated by moderate or worse dysfunction on any International Index of Erectile Function (IIEF) domain, history of seizure disorder, history of previous chemotherapy or radiation, current psychiatric disorder or history of bipolar disorder, family history (including cousins and grandparents) of bipolar disorder (manic depressive disorder) or suicide, use of any psychotropic agents (prescription or herbal) or anticonvulsants, use of sleeping pills more than once per week, use of any hormonal medications on a daily or intermittent basis including glucocorticoid pills, inhalers, or creams during the preceding 3 months, use of medications which may affect hormonal measures or sexual function, use of any prescription or non-prescription medications to enhance sexual function, inability to read, follow instructions or complete questionnaires in English, consumption of more than 2 ounces of alcohol daily, and consumption of tobacco or illicit drugs.

Statistical Analysis Plan

After consultation with a biostatistician, the required sample size for a proportion difference of 5% of patients with abnormal sperm DNA fragmentation in the control group and 30% of patients with abnormal sperm DNA fragmentation in the treatment group with 80% power, two-sided alpha 5% is 35 patients per group. Descriptive statistics (including mean, standard deviation, median, range, frequency, and percent) for demographic and clinical factors of interest will be calculated for the placebo and treatment groups separately. The two-sample t-test (or Wilcoxon rank-sum test) and chi-square test (or Fisher's exact test) will be used to compare 1) mean (median) TUNEL values and 2) proportions of patients with TUNEL values >25%, respectively, between the treatment and placebo groups, at each time point. Analysis of covariance (ANCOVA) and multiple logistic regression will also be used to compare mean TUNEL value and proportion of patients with TUNEL values > 25%, respectively, between the two groups, after adjustment for baseline value (i.e., assuming any remaining imbalance in the baseline assessment between the two groups after randomization). The paired t-test and McNemar's chi-square test will be used to compare change in mean TUNEL value and change in proportion of abnormal results,

respectively, between the time points, within each group separately. The secondary outcomes of interest will also be compared between the two groups using similar statistical tests as noted above. All p-values will be two-sided with statistical significance evaluated at the 0.05 alpha level. Ninety-five percent confidence intervals (95% CI) will be calculated to assess the precision of the obtained estimates. All analyses will be performed in SAS Version 9.4 (SAS Institute, Inc., Cary, NC) and Stata Version 14.0 (StataCorp, College Station, TX).

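### The SAP tests TUNEL as a mean and as a proportion at every visit, each at 0.05, and names no deciding visit, measure, model or multiplicity rule

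*Combined protocol and SAP*

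**What the plan says.** Under Primary and Secondary Objectives, the aim is stated as "The primary objective of the research study is to determine the administration of duloxetine on sperm DNA fragmentation", with no scale, visit or contrast. Study Design lists five samples: "semen analyses at baseline before administration, at 2-weeks, 6-weeks, and then at 2-weeks and 4-weeks after drug cessation". Four of these are post-baseline.

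The Statistical Analysis Plan sizes the trial on a binary measure: the "required sample size for a proportion difference of 5% of patients with abnormal sperm DNA fragmentation in the control group", against 30% under treatment, with 80% power, where "two-sided alpha 5% is 35 patients per group". That sentence names no visit and does not define abnormal. A later phrase, "change in mean TUNEL value and change in proportion of abnormal results", suggests that abnormal means TUNEL above 25%.

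The SAP then compares the mean (or median) and the proportion above 25% "between the treatment and placebo groups, at each time point", using a t-test or Wilcoxon test for the first and chi-square or Fisher's exact test for the second. It gives no rule for choosing within either pair. It goes on: "Analysis of covariance (ANCOVA) and multiple logistic regression will also be used", with adjustment for baseline. Within-arm paired tests follow. One threshold covers everything: "All p-values will be two-sided with statistical significance evaluated at the 0.05 alpha level". Confidence intervals at 95% are also planned.

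**The concern.** The plan has a sample size that assumes one test at 5%, and an analysis section that runs many tests at 5% and ranks none of them. Two things follow.

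First, there is no rule to stop any one significant TUNEL result from being read as confirming the hypothesis. Read that way, the chance of a false finding exceeds the 5% on which 35 per group rests.

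Second, even a reader who accepts the proportion as the intended primary measure cannot tell which visit decides, or whether the unadjusted test or the logistic model does. If the 2-week and 6-week results differ, or on-treatment and post-cessation results differ, the plan does not say whether the hypothesis was supported. The confidence intervals describe precision at each visit; they do not settle which visit counts.

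**Working it through.** **Inputs from the document.** Abnormal rates 5% and 30%; two-sided alpha 0.05; power 80%; 35 per group; four post-baseline samples; two TUNEL measures.

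**The plan's own figure.** Pooled formula, no continuity correction, with mean rate (0.05 + 0.30)/2 = 0.175:

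n = [1.960 × √(2 × 0.175 × 0.825) + 0.842 × √(0.05 × 0.95 + 0.30 × 0.70)]² / 0.25² = (1.053 + 0.427)² / 0.0625 = 35.06.

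This agrees with the stated 35, allowing for rounding. Power at 35 is Φ[(0.25 × √35 − 1.053)/0.507] = Φ(0.839) = 79.9%. The sample size is sound for a single test at 0.05.

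**Number of tests.** 2 measures × 4 visits = 8 unadjusted between-arm tests. Baseline comparisons, adjusted models, within-arm tests and secondary outcomes are not counted.

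**False-positive chance if any of the eight counts.** Were the tests independent, it would be 1 − 0.95⁸ = 33.7%. They are correlated, so this was simulated with 35 per arm and no drug effect. The assumptions, none of them in the document, are between-visit correlation 0.3 to 0.8 (exchangeable or first-order autoregressive), normal TUNEL, and a null abnormal rate equal to the plan's control rate of 5%. The SAP permits chi-square or Fisher, so both readings are shown: Fisher when an expected count is below 5, and chi-square throughout.

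| Tests that may count | Fisher switch | Chi-square throughout |
|---|---|---|
| All 8, either direction | 12-19% | 20-28% |
| All 8, deterioration only (one test: 2.5% nominal) | 6-10% | 10-15% |
| Proportion alone, 4 visits | about 1% | 12-14% |
| Mean alone (t-test), 4 visits | 12-18% | same |

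The contrast in the third row comes from the size of a single proportion test at a 5% null rate: exactly 0.3% with the switch, against 3.6% with chi-square. With the switch, the inflation comes almost entirely from testing the mean repeatedly. With chi-square throughout, the repeated proportion tests add materially as well.

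**Disagreement between visits if the drug works as planned.** Take 5% v 30% at both 2 and 6 weeks, which under normality is a shift of 1.12 SD. With the Fisher switch, each proportion test has about 80% power, and the two verdicts differ in 21-29% of trials. The t-tests have about 99.6% power at that shift and differ in under 1%.

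**One test only.** For the proportion at one visit with the Fisher switch, exact power at 35 per group is 80.4%. Exact size is 0.3% at a 5% null rate, 4.4% at 17.5%, and at most 5.2% at any null rate up to 50%. Fisher's test used always would have 74.1% power.

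**The case against.** The best reply is that the sample-size sentence already points to one binary contrast, that the SAP never says any significant result is a success, and that confidence intervals allow an estimation-based reading. The first part stands as far as the measure goes: the proportion is evidently what was powered. But the sentence gives no visit and no model, so four visits and two analyses of the proportion remain.

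The second part also stands. A reader might infer that the plan defines success as any significant TUNEL result, so that its error rate simply is 12-28%. The text does not say this. It sets one threshold for all p-values and is silent on how they combine, so the inflation is conditional on that use.

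Three further limits hold. The stated hypothesis is deterioration, so a significant result favouring duloxetine would not support it; false support is about half the two-sided rate. The claim that only the mean causes the inflation depends on the Fisher switch, which the SAP does not state. And frequent disagreement between visits is a feature of the proportion, not of the mean, and assumes equal effects at 2 and 6 weeks, which the document does not specify.

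A reader might also infer that 35 per group is wrong. It is not; it reproduces for one test at 0.05.

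**Conclusion.** The gap is real: no section names a deciding TUNEL visit, measure, model or multiplicity rule, and no redaction or missing figure accounts for it. If any significant result is taken as support, the two-sided error over the eight unadjusted tests is 12-19% or 20-28%, depending on which permitted test is used for the proportion. In the deterioration direction it is 6-10% or 10-15%, against 2.5%. These ranges rest on the assumed correlation, normality and a 5% null rate. Separately, and without that reading of success, a drug effect of the planned size at both on-treatment visits would leave the proportion tests in conflict in 21-29% of trials with the Fisher switch, with nothing in the plan to resolve it. The documents do not support saying that the plan endorses selective claims or that its sample size is faulty.

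**What to change.** Before unblinding, state in the SAP one primary test (one measure, one visit, one model) at two-sided 0.05.

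- **Measure and model.** The choice that keeps the stated sample size is the proportion with TUNEL above 25%, treatment v placebo, unadjusted, by chi-square or by Fisher's exact test when an expected count is below 5. Say that this is what abnormal means in the sample-size sentence.
- **Visit.** The 6-week sample, at the end of randomised treatment, is the natural candidate. The sponsor should confirm it against the week-six dose reduction described in Study Design.
- **Everything else.** Report all other TUNEL comparisons, including baseline-adjusted ANCOVA, as secondary estimates with 95% confidence intervals and no confirmatory claim. Testing ANCOVA at 0.05 only after a significant primary result is optional.

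The cost is wording; no patients or data are added. By comparison, letting all eight tests decide under Bonferroni (0.05/8 = 0.00625) would need 58 per group by the same pooled formula, and would leave 50.8% power at 35.

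The downside is that, under the planned effect and normality, the mean is significant but the proportion is not in about 19-20% of trials, and that result could not be claimed as confirmatory. A sponsor who finds this too costly could name the continuous measure instead, but would then need a sample-size basis for it.

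Study Design is partly in the past tense. If data are already unblinded, the choice should be labelled post hoc.

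### The plan runs unadjusted and baseline-adjusted TUNEL comparisons side by side at 0.05, ties adjustment to imbalance, and never says which result is the reported arm effect

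*Combined protocol and SAP*

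**What the plan says.** All of this is in the combined protocol and SAP. Under Statistical Analysis Plan, the unadjusted comparisons come first: "The two-sample t-test (or Wilcoxon rank-sum test) and chi-square test (or Fisher's exact test) will be used to compare" mean or median TUNEL and the proportion above 25%, "between the treatment and placebo groups, at each time point". Baseline is not excepted. Under Study Design, baseline is the first of the listed semen assessments, and the Methods text describes DNA fragmentation as assessed "at numerous time points before, during, and after drug administration". A between-arm test at baseline therefore follows from the wording.

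The next sentence adds ANCOVA for the mean and multiple logistic regression for the proportion, to be used as well, "after adjustment for baseline value (i.e., assuming any remaining imbalance in the baseline assessment between the two groups after randomization"). Imbalance is the only reason given for adjusting. Secondary outcomes are to be handled with similar tests, and every p-value is two-sided and judged at 0.05.

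The section does not rank the adjusted and unadjusted results. It also gives no balance threshold and no condition under which the adjusted model would be dropped.

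**The concern.** Two analyses of the same arm difference, each judged at 0.05 and neither designated, leave the choice of result open until the data are seen. The two can disagree, and the plan does not say which then stands.

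The stated reason for adjusting makes this worse. In a randomised trial, baseline adjustment of a continuous outcome is worth doing because it removes the outcome variance that baseline explains. That gain does not depend on whether the arms happen to differ at baseline. An analyst who takes the imbalance wording as guidance, with a baseline test to hand, could set ANCOVA aside in just those trials where the arms look alike. The baseline test itself is uninformative: between properly randomised arms, any difference is due to chance.

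At stake are the error rate of the claim on mean TUNEL, the width of its interval, and the same for each continuous secondary outcome with a baseline value.

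**Working it through.** **Inputs from the documents.** Control rate: "5% of patients with abnormal sperm DNA fragmentation in the control group". Treatment rate: "30% of patients with abnormal sperm DNA fragmentation in the treatment group". The required number "with 80% power, two-sided alpha 5% is 35 patients per group".

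**Inputs assumed.** The baseline-to-follow-up correlation r of TUNEL is not given; 0.3, 0.5 and 0.7 are used. TUNEL is taken as normal with equal variances. The true shift is set at 0.5 SD for the power figures, since the documents give no SD and no mean difference. The trigger for the conditional reading is baseline p<0.05, since the plan states none.

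**The plan's own figure.** With p1 = 0.05, p2 = 0.30 and mean 0.175, the pooled formula is

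n = [1.960 × √(2 × 0.175 × 0.825) + 0.842 × √(0.05 × 0.95 + 0.30 × 0.70)]² / 0.25² ≈ 35.06 per arm.

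This is 36 when rounded up, and power at 35 per arm is 79.9%. The stated 35 reproduces, and it rests on an unadjusted comparison of proportions.

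**Precision from ANCOVA.** Residual variance is multiplied by 1 − r²:
- r = 0.3: 0.91, a fall of 9%; equivalent to 35/0.91 = 38.5 per arm unadjusted.
- r = 0.5: 0.75, a fall of 25%; 35/0.75 = 46.7 per arm.
- r = 0.7: 0.51, a fall of 49%; 35/0.51 = 68.6 per arm.

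Observed balance does not enter these expressions.

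**Type I error if either result may be claimed.** Under no effect, the unadjusted and adjusted test statistics have correlation of about √(1 − r²), that is 0.95, 0.87 and 0.71. They are close but not identical, so taking the smaller p-value exceeds 5%. Simulation used 20,000 trials per setting, 35 per arm, one time point. The Monte Carlo standard error is about √(0.05 × 0.95/20,000) = 0.15 percentage points.

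| No true effect: rejection rate | r = 0.3 | r = 0.5 | r = 0.7 |
|---|---|---|---|
| ANCOVA always | 5.0% | 5.0% | 5.0% |
| Either may be claimed | 6.3% | 7.4% | 8.2% |
| ANCOVA only if baseline p<0.05 | 4.7% | 4.4% | 3.7% |

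**Power at the assumed 0.5 SD shift.**

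| | r = 0.3 | r = 0.5 | r = 0.7 |
|---|---|---|---|
| Unadjusted t-test | 54% | 54% | 54% |
| ANCOVA only if baseline p<0.05 | 54% | 55% | 55% |
| ANCOVA always | 57% | 66% | 82% |
| Trials in which the two tests disagree | 10% | 19% | 32% |

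The conditional rule gains almost nothing because its trigger fires in only about 5% of randomised trials. Its error rate below 5% shows that its intervals are too wide.

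**Binary outcome.** Expected control events are 0.05 × 35 = 1.75, about 2 men. Neither 1 − r² nor the tables apply to TUNEL >25%. Logistic adjustment changes the odds ratio being estimated, and may be unstable with so few events.

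**The case against.** A reader might infer that the plan adjusts only when baselines differ, so that with balanced arms the unadjusted test decides and most of the baseline information is wasted. The documents do not support that. The main verb commits to the adjusted models in addition to the unadjusted tests, and the parenthesis reads as an explanation, not a condition. If both results are reported in full, the narrower ANCOVA interval is always available and no precision is lost. This objection stands, so the conditional-rule rows show only what would follow if the clause were applied that way.

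The 0.5 SD shift can also be challenged. If 5% and 30% are tail areas of normal distributions with equal variance beyond one cut-off, the implied shift is 1.645 − 0.524 = 1.12 SD. The unadjusted t-test then has about 99.6% power at 35 per arm, and ANCOVA can add almost nothing to power. That also stands: the power gain matters only for smaller effects, and at r = 0.3 it is about 3 points even at 0.5 SD. The narrower interval and the error rate under no effect do not depend on the assumed shift.

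Finally, no decision is tied to the baseline test, so taken alone it is a minor matter.

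None of this supplies the missing statement of which result is the arm effect. Under the plainer reading, with both analyses run, that omission is what allows the error rate to exceed 5%.

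**Conclusion.** The point holds as an undefined choice between two analyses, with a mistaken reason given for one of them. It does not hold as a claim that the plan gates adjustment on imbalance or lets the unadjusted test decide.

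For mean TUNEL at a single time point, leaving the choice open allows a type I error of roughly 6% to 8% in place of 5%, for r between 0.3 and 0.7. Fixing ANCOVA in advance holds 5% and narrows the interval by a factor of √(1 − r²), from 0.95 down to 0.71. These sizes rest on normal data, 35 per arm and an r that the documents do not give. At low r the benefit is modest.

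The reasoning extends to continuous secondary outcomes with a baseline value. For TUNEL >25%, the lack of a designated analysis is the same gap, but its size has not been calculated here. Choices between time points, or between the mean and the proportion, are not counted in these figures.

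**What to change.** In the Statistical Analysis Plan section:

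1. Delete the parenthesis that gives remaining imbalance as the reason for adjustment.
2. State that, for mean TUNEL and each continuous secondary outcome with a baseline value, the baseline-adjusted ANCOVA is always fitted and is the reported arm effect, with its 95% confidence interval. Label the unadjusted tests supportive.
3. Limit between-arm tests to post-baseline time points, and present baseline by arm descriptively only.
4. For TUNEL >25%, name one analysis in advance as the reported one. If it is the logistic model, say that its odds ratio is conditional on baseline, and say what will be done if sparse control events make the fit unstable.

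The cost is SAP wording only, with no new data, visits or patients. The change carries most weight if made before outcomes are compared by arm.

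### Change in TUNEL between visits is tested only within each arm, so no planned estimate shows whether the difference between arms changes after the drug is stopped (minor, supporting analysis)

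*Combined protocol and SAP*

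**What the plan says.** Study Design schedules semen samples at baseline, "at 2-weeks, 6-weeks, and then at 2-weeks and 4-weeks after drug cessation", in both arms. It also states: "In the sixth and last week of therapy, the drug dosage will be halved to 30mg PO daily as a taper". Methods adds: "Changes in sperm DNA fragmentation will be assessed at numerous time points before, during, and after drug administration".

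The Statistical Analysis Plan handles TUNEL in three ways:

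- **Levels between arms.** Mean (or median) TUNEL and the proportion above 25% are compared between duloxetine and placebo at each visit. That includes both visits after stopping.
- **Baseline-adjusted comparison.** ANCOVA and logistic regression compare the two measures "between the two groups, after adjustment for baseline value". The visits are not listed.
- **Change between visits.** Paired t-tests and McNemar tests are run "respectively, between the time points, within each group separately". The pairs of visits are not listed.

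Two general sentences apply throughout: "All p-values will be two-sided with statistical significance evaluated at the 0.05 alpha level" and "Ninety-five percent confidence intervals (95% CI) will be calculated to assess the precision of the obtained estimates". The within-arm tests are not labelled descriptive. No arm-by-visit term, difference in change, or model adjusted for an on-drug value is planned.

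**The concern.** Two of the five samples are taken after the drug is stopped, so a reader of the results will naturally ask whether a duloxetine effect fades. The only planned analysis that addresses change from one visit to another looks at each arm alone. If TUNEL falls in the duloxetine arm after stopping, a paired test cannot say whether that is due to the drug or to something that moves both arms, such as repeat sampling or laboratory drift. The placebo men give samples at the same visits, so the trial already holds the control for such a trend but does not use it for this question.

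At stake is the support for any statement about change after stopping. As planned, it would rest on within-arm p-values or on separate visit-by-visit results set side by side. The choice of visits also matters. The 2-week sample precedes the dose reduction and the 6-week sample does not, so the two on-drug visits are not interchangeable, and the plan does not say which one is the starting point.

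**Working it through.** **The plan's own figure.** The sample size rests on a "proportion difference of 5% of patients with abnormal sperm DNA fragmentation in the control group" and 30% in the treatment group, with 80% power and two-sided alpha 5%. With pooled variance and mean proportion 0.175:

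n = [1.960 × √(2 × 0.175 × 0.825) + 0.842 × √(0.05 × 0.95 + 0.30 × 0.70)]² / 0.25² = 35.06 per group.

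That is 36 when rounded up, and power at 35 is 79.9%. The stated 35 reproduces, and nothing below alters it.

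**What each planned analysis estimates.** Let D(v) be the duloxetine minus placebo difference in mean TUNEL at visit v.

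- The per-visit tests estimate D(v) for each v.
- ANCOVA estimates D(v) adjusted for baseline.
- The paired t-test estimates the mean change between two visits in one arm. That is any drug-related change plus any trend shared by the arms.
- The quantity of interest after stopping is D(post) − D(on), which equals the mean change on duloxetine minus the mean change on placebo. A shared trend cancels in it.

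No planned analysis reports that last quantity. Its point estimate follows by subtracting two per-visit differences. Its confidence interval does not, because it needs the within-man covariance, which separate per-visit tests do not give.

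**Precision of the missing contrast.** The documents give no SD or correlation for TUNEL, so results are in units of the SD of change.

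- Half-width of the 95% CI = t(0.975; 2n − 2) × √(2/n).
- 35 per arm: 1.995 × 0.239 = 0.477.
- 28 per arm with both samples (20% loss, assumed): 2.005 × 0.267 = 0.536.
- True difference giving 80% power (noncentral t): 0.679 at 35 per arm, 0.762 at 28.

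To convert to units of the TUNEL SD at a single visit, with equal SDs and visit correlation r, multiply by √(2(1 − r)):

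| Assumed r | Factor | Half-width at 35 per arm (TUNEL SD) |
|---|---|---|
| 0.3 | 1.183 | 0.564 |
| 0.5 | 1.000 | 0.477 |
| 0.7 | 0.775 | 0.369 |

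**Illustration only: comparing within-arm p-values across arms.** Suppose there is no drug effect, both arms share a true change of d (in SDs of change), and each arm has 35 complete pairs. Let p be the power of the paired t-test. The chance that duloxetine alone is significant is p(1 − p):

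| d | p | p(1 − p) |
|---|---|---|
| 0 | 0.050 | 0.048 |
| 0.1 | 0.089 | 0.081 |
| 0.2 | 0.210 | 0.166 |
| 0.34 | 0.498 | 0.250 |
| 0.5 | 0.820 | 0.148 |
| 0.8 | 0.996 | 0.004 |

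A direct between-arm test of the change rejects in about 5% of trials at every d. The table shows why the within-arm tests should not be read against each other. The plan does not say that they will be.

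**The case against.** The strongest reply is that the trial does not ask this question. Its hypothesis is deterioration on duloxetine. No recovery objective or endpoint appears, and the Methods sentence on assessment before, during and after treatment can be read as a description of when samples are taken. This stands. It is why the contrast is offered as supporting.

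Second, the arms are already compared at both visits after stopping, under a general promise of confidence intervals, and those comparisons are free of a shared trend. This also stands. At the design effect they may even suffice for full recovery. If TUNEL is normal with equal SDs, 5% against 30% abnormal implies a shift of 1.645 − 0.524 = 1.12 SD. With complete recovery, the on-drug and post-drug intervals (each about ±0.48 SD) fail to overlap in about 73% to 80% of simulated trials at visit correlations of 0.3 to 0.7. The direct contrast detects the change in about 97% to 100%, and it matters more when recovery is partial.

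Third, on-drug to off-drug pairs are an inference. The plan says only that change between time points is tested, and the tests could run from baseline to each visit. That is fair, but it leaves the same gap: on either reading, change is examined only within arms and the pair is unnamed.

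Fourth, the discordance table describes a practice that the plan does not state, and its 25% peak needs a particular shared trend for which the documents give no evidence. Agreed. It is an illustration only.

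**Conclusion.** The point holds in a narrow form and is minor. The plan has no between-arm estimate with a confidence interval of how the TUNEL difference changes once the drug is stopped, and its only tests of change between visits are uncontrolled. The absence is clear from the text. Its practical weight depends on whether anyone makes a statement about change after stopping.

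A reader might infer three stronger things, none of which the documents support:

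- **No randomised comparison after stopping.** There is one at each of the two visits.
- **A weakened primary analysis or sample size.** Neither depends on the within-arm tests.
- **A false-positive rate of up to 25%.** That figure belongs to a comparison of within-arm p-values that the plan does not propose, at one assumed trend. With no shared trend it is about 5%.

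The precision figure of ±0.48 SD of change assumes 35 complete pairs per arm and equal SDs of change. On the scale of the TUNEL SD it ranges from ±0.37 to ±0.56 over assumed visit correlations of 0.7 to 0.3.

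**What to change.** Amend the Statistical Analysis Plan in a few sentences:

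1. Keep the between-arm comparisons, including the baseline-adjusted ones, as the test of deterioration.
2. State that the within-arm paired t-tests and McNemar tests are descriptive.
3. Add one supporting contrast: the between-arm difference in change in continuous TUNEL from one named on-drug visit to one named visit after stopping, with its 95% CI. The 6-week sample to the sample 4 weeks after cessation is one option. Fix the pair before unblinding, and note how the starting visit relates to the taper. If unblinding has already happened, label the contrast post hoc.
4. Base any statement about change after stopping on that contrast.

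A two-sample comparison of change scores is enough with complete pairs. Its standard error is √(SE₁² + SE₂²), from the standard errors that the two paired t-tests already produce. A repeated-measures mixed model with arm, visit, arm-by-visit and baseline TUNEL is optional and would also use men with one of the two samples missing. No extra model for TUNEL above 25% is needed.

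The cost is slightly more analysis, with no new samples, visits or software. The limit is precision: 80% power needs a difference of about 0.68 SD of change at 35 per arm, or 0.76 at 28. The report should say that an interval including zero does not show that an effect persists.
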